1.2.11 Outcomes

Individual level data from patients in all participating ICUs will be obtained from the HCA corporate data warehouse, including demographics, census (including ICU patient days), bathing queries, pharmacy (nasal decolonization product administration), diagnostic and procedure codes (enabling comorbidity score assessment), and microbiology testing results.

The primary outcome will be *S. aureus* clinical cultures (MRSA and MSSA) attributed to the participating ICU (>2 days into the ICU stay until 2 days after ICU discharge). Secondary outcomes intended for primary manuscript, include: 1) ICU-attributable MRSA clinical cultures, 2) ICU-attributable all-cause bloodstream infection.

Table 6. Mupirocin-Iodophor Swap Out Trial Outcomes

Outcome	Metric
Primary Trial Outcome	ICU-attributable S. aureus clinical cultures (MRSA + MSSA)
Secondary Trial Outcomes	ICU-attributable MRSA clinical cultures ICU-attributable all-cause bloodstream infection

1.2.12 Data Collection

Descriptive data, outcome data and variables for addressing confounding will be derived from microbiology, census, pharmacy, and claims data from participating hospitals. The following data elements will be collected (Table 6) using encrypted study IDs.

Table 6. Data Elements

Source Data	Result Types	Elements
Microbiology: Finalized Results	All positive and negative cultures	Pathogen name (if culture is positive), patient identifier, date of collection, body site of collection, antimicrobial susceptibility
Census Data	Line item per admission	Patient identifier, hospital admission date, hospital discharge date, ICU vs. non-ICU charge code by calendar date, age in years, gender
Claims Data	Line item per admission	For case mix adjustment: Diagnosis codes (ICD9-ICD10) Procedure codes (ICD9/ICD10/CPT codes)
Pharmacy	Mupirocin and iodophor dispensing	Patient identifier, date range dispensed, ICU location

Nursing Queries	Bathing responses	Data on whether a bath was given, and if yes, with a CHG or non-CHG bathing soap product.
-----------------	-------------------	---

We will use claims data to collect diagnostic and procedure codes that will be used for case mix adjustment for both hospital-wide, ICU-specific, and post-ICU outcomes. Case mix will be assessed using a comorbidity score (e.g. Elixhauser score) as well as evaluating the individual components of that score (e.g. diabetes, renal disease) and evidence of major surgery.

1.2.13 Statistical Analysis and Power

The primary analysis will be an as-randomized proportional hazards model to evaluate for noninferiority at a margin of 10% (difference in relative hazard). Model terms will include arm, period (baseline vs. intervention) and an arm by period interaction term to assess whether the difference in relative hazard between the baseline and intervention period differs significantly between the two arms. Clustering within hospital will be accounted for using shared frailties, i.e., a random intercept for each hospital, and, if it should become technologically feasible, an additional random intercept for each ICU within hospital and for repeated hospital stays for each person.

- Null hypothesis (H_0): the change in relative hazard of clinical culture of *S. aureus* in the Iodophor-CHG arm is higher than (inferior to) the change in the Mupirocin-CHG arm by more than 10%
- Alternative hypothesis (H_1): the change in relative hazard of clinical culture of *S. aureus* in the Iodophor-CHG arm is higher than (inferior to) the Mupirocin-CHG arm by 10% or less

Phase-in period data will not be included in the analysis.

To be explicit, the primary analysis will take the form of $\lambda_{ij}(t) = \lambda_0(t)e^{\beta_1 Arm_{ij} + \beta_2 Per_{ij} + \beta_3 Arm_{ij} * Per_{ij} + \gamma_i}$ where $\lambda_{ij}(t)$ is the time t of the *S. aureus* clinical culture for person j at hospital i . The baseline hazard function for time t , $\lambda_0(t)$, is shared by all people; γ_i is the frailty shared by patients at hospital i . The linear predictor in the exponent functions as in a linear model, where Arm_{ij} indicates the treatment arm of person j in hospital i is the iodophor arm, and Per_{ij} indicates that person j in hospital i was seen in the intervention period. Thus β_3 is the estimated differential effect of iodophor relative to mupirocin in the intervention period compared to baseline. While software is currently not able to include frailties for multiple visits per person or for multiple ICUs per hospital on the scale of the data, we will include them if this should become possible by the time the trial is analyzed.

The primary outcome of the trial is ICU-attributable *S. aureus* clinical cultures (MRSA + MSSA) where ICU-attributable is defined as *S. aureus* cultures occurring in specimens collected from study cohort patients from the 3rd day of an ICU stay through 2 days after ICU discharge. This outcome will be assessed using an as-randomized unadjusted proportional hazards model as described above with two-sided significance set at alpha = 0.05, consistent with FDA standards of non-inferiority (<https://www.fda.gov/regulatory-information/search-fda-guidance-documents/non-inferiority-clinical-trials>). The pre-specified non-inferiority margin, we repeat, is 10%.

There is reason to suspect that nasal iodophor may be inferior to mupirocin due to FDA clearance based upon suppression versus cidal kill for *S. aureus*, which is the reason for the non-inferiority trial. However, conversely, if iodophor is found to be non-inferior, we are declaring the a priori intent to assess for superiority because of evidence of mupirocin-resistant *S. aureus* strains where none is expected to exist for iodophor. For this reason, if iodophor is found to be non-inferior in the primary outcome of the trial, we will also report the pre-specified assessment of superiority which is already performed in the primary analysis.

Secondary non-inferiority outcomes include 1) ICU-attributable MRSA clinical cultures and 2) ICU-attributable all-cause bloodstream infection. These will be assessed using an as-randomized unadjusted proportional hazards model as described above. We will use two-sided significance tests set at alpha = 0.05 for each outcome to determine possible inferiority with greatest possible sensitivity, again with a non-inferiority margin of 10%. Due to the above antibiotic-resistance rationale to suspect possible superiority, if non-inferiority is met for these secondary outcomes, we will perform a pre-specified assessment of superiority at a two-tailed significance set at alpha = 0.025, which accounts for the multiple comparisons of two outcomes. To be clear, the non-inferiority tests are not adjusted for multiple testing, while the superiority tests, if they are performed, will be adjusted for multiple testing, for conservatism.

Additional analyses will include as-treated and adjusted models, which will be reported as point estimates with confidence intervals without p-values. The reason for including these analyses is to provide additional information related to the trial outcomes for reader assessment of potential confounders. The reason to not include them in a formal multiple comparisons adjustment is because these analyses are non-independent evaluations related to the as-randomized unadjusted analyses.

While 140 HCA hospitals are eligible for recruitment, we have HCA corporate commitment to assure the participation of at least 120 hospitals. Power was assessed using simulation methods. We simulated hospitals using information from HCA regarding ICU size and from a prior trial (REDUCE MRSA Trial) regarding likely rates of *S. aureus* in the baseline period. With 120 hospitals, we will have 82% power to detect non-inferiority within a hazard ratio of 1.1, based upon 2014 HCA ICU-attributable *S. aureus* clinical cultures of 4.8 cases per 1,000 ICU-days. While the intent is to confirm non-inferiority, we assume that iodophor will eradicate 5% more *S. aureus* than mupirocin due to existing mupirocin resistance. We estimate that total ICU patients in the intervention period will be ~171,500 patients who stay >2 ICU days.

References

- ¹ Fagan RP, Edwards JR, Park BJ, Fridkin SK, Magill SS. Incidence trends in pathogen-specific central line-associated bloodstream infections in US intensive care units, 1990-2010. *Infect Control Hosp Epidemiol*. 2013 Sep;34(9):893-9.
- ² Burton DC, Edwards JR, Srinivasan A, Fridkin SK, Gould CV. Trends in catheter-associated urinary tract infections in adult intensive care units-United States, 1990-2007. *Infect Control Hosp Epidemiol*. 2011 Aug;32(8):748-56.
- ³ Burton DC, Edwards JR, Horan TC, Jernigan JA, Fridkin SK. Methicillin-resistant *Staphylococcus aureus* central line-associated bloodstream infections in US intensive care units, 1997-2007. *JAMA*. 2009 Feb 18;301(7):727-36.
- ⁴ Huang SS, Septimus E, Kleinman K, Moody J, Hickok J, Avery TR, Lankiewicz J, Gombosev A, Terpstra L, Hartford F, Hayden MK, Jernigan JA, Weinstein RA, Fraser VJ, Haffenreffer K, Cui E, Kaganov RE, Lolans K, Perlin JB, Platt R; CDC Prevention Epicenters Program; AHRQ DECIDE Network and Healthcare-Associated Infections Program. Targeted versus universal decolonization to prevent ICU infection. *N Engl J Med*. 2013;368(24):2255-65.

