The primary outcome of the trial is ICU-attributable *S. aureus* clinical cultures (MRSA + MSSA) where ICU-attributable is defined as *S. aureus* cultures occurring in specimens collected from study cohort patients from the 3rd day of an ICU stay through 2 days after ICU discharge. This outcome will be assessed using an as-randomized unadjusted proportional hazards model as described above with two-sided significance set at alpha = 0.05, consistent with FDA standards of non-inferiority (<https://www.fda.gov/regulatory-information/search-fda-guidance-documents/non-inferiority-clinical-trials>). The pre-specified non-inferiority margin, we repeat, is 10%.

There is reason to suspect that nasal iodophor may be inferior to mupirocin due to FDA clearance based upon suppression versus cidal kill for *S. aureus*, which is the reason for the non-inferiority trial. However, conversely, if iodophor is found to be non-inferior, we are declaring the a priori intent to assess for superiority because of evidence of mupirocin-resistant *S. aureus* strains where none is expected to exist for iodophor. For this reason, if iodophor is found to be non-inferior in the primary outcome of the trial, we will also report the pre-specified assessment of superiority which is already performed in the primary analysis.

Secondary non-inferiority outcomes include 1) ICU-attributable MRSA clinical cultures and 2) ICU-attributable all-cause bloodstream infection. These will be assessed using an as-randomized unadjusted proportional hazards model as described above. We will use two-sided significance tests set at $\alpha = 0.05$ for each outcome to determine possible inferiority with greatest possible sensitivity, again with a non-inferiority margin of 10%. Due to the above antibiotic-resistance rationale to suspect possible superiority, if non-inferiority is met for these secondary outcomes, we will perform a pre-specified assessment of superiority at a two-tailed significance set at $\alpha = 0.025$, which accounts for the multiple comparisons of two outcomes. To be clear, the non-inferiority tests are not adjusted for multiple testing, while the superiority tests, if they are performed, will be adjusted for multiple testing, for conservatism.

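### Should the two secondary non-inferiority tests be adjusted for multiplicity, or made to wait for the primary result?

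*Protocol*

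**What the plan says.** Protocol section 1.2.13 and the Analysis section of the SAP give the same rules.

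- **Hypotheses.** Under the null, the change in hazard in the iodophor arm "is higher than (inferior to) the change in the Mupirocin-CHG arm by more than 10" per cent. Rejecting it declares non-inferiority. The rule is written for *S. aureus* cultures and carried to the secondaries by reference to the same model.
- **Test of a difference.** The arm-by-period term is also there "to assess whether the difference in relative hazard between the baseline and intervention period differs significantly between the two arms".
- **Secondary non-inferiority.** MRSA cultures and all-cause bloodstream infection are each tested at two-sided 0.05 with the 10% margin, "for each outcome to determine possible inferiority with greatest possible sensitivity". The SAP adds that "the non-inferiority tests are not adjusted for multiple testing".
- **Secondary superiority.** "if non-inferiority is met for these secondary outcomes, we will perform a pre-specified assessment of superiority", at two-sided 0.025 each.
- **Conditions.** Primary non-inferiority precedes primary superiority, and secondary non-inferiority precedes secondary superiority. Nothing ties a secondary test to the primary result.
- **Power.** The only figure is for the primary: "82% power to detect non-inferiority within a hazard ratio of 1.1", where "we assume that iodophor will eradicate 5% more" *S. aureus* than mupirocin.

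**The concern.** Three things look wrong together.

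1. The stated reason seems to point the wrong way. When the null is that iodophor is too much worse, relaxing alpha helps a non-inferiority claim and does not guard against inferiority. The plan also writes down no explicit rule for declaring inferiority.
2. The plan halves alpha for the two secondary superiority tests but not for the two secondary non-inferiority tests, although confirming non-inferiority is its main aim.
3. If the primary fails, a formal non-inferiority claim on MRSA or bloodstream infection remains open, and the plan does not say how to read it.

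At stake is a formal claim of non-inferiority on a prominent outcome, in a trial whose primary objective was missed, under a rule described as the cautious choice.

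**Working it through.** **Inputs from the documents.** Margin HR 1.10; two-sided 0.05 for each non-inferiority test; two-sided 0.025 for each secondary superiority test; 82% primary power; an assumed 5% advantage for iodophor, taken here as HR 0.95.

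**Assumed, because the documents do not say.**
- Two-sided 0.05 means the upper 95% limit is compared with 1.10, so each test is one-sided 0.025.
- Correlations between test statistics: primary–MRSA 0.5 to 0.8 for error rates; primary–bloodstream infection 0.2; MRSA–bloodstream infection 0.15.
- Secondary standard errors equal to the primary's or 1.5 times larger.

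**The plan's own figures.** The superiority alpha reproduces: 0.05/2 = 0.025. The 82% power cannot be rebuilt uniquely, because ICU-days per patient and between-hospital variance are not given. It does imply a standard error for the log hazard ratio:

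SE = (ln 1.10 − ln 0.95)/(1.960 + 0.915) = (0.0953 + 0.0513)/2.875 = 0.051

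**Does the stated reason fit?** Compare two rules, with z = 1.960 (two-sided 0.05) or 2.241 (two-sided 0.025), at SE 0.051.

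- Declare non-inferiority: Φ(ln(1.10/HR)/SE − z)
- Find harm, lower limit above 1: Φ(ln(HR)/SE − z)

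| True HR | Rule | Alpha 0.05 | Alpha 0.025 |
|---|---|---|---|
| 1.05 | declare non-inferiority | 14.7% | 9.2% |
| 1.10 | declare non-inferiority | 2.5% | 1.25% |
| 1.10 | lower limit above 1 | 46% | 35% |
| 1.15 | lower limit above 1 | 78% | 69% |

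The reason is wrong for the first rule and right for the second. At 1.5 times the SE (0.0765), harm detection at HR 1.15 is 45% against 34%, the same direction.

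**How large is the unadjusted error?** Put both secondaries exactly at HR 1.10.

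- Upper bound for any false secondary claim: 2 × 0.025 = 5.0%
- If independent: 1 − 0.975² = 4.9%; with correlation 0.15, also 4.9%
- Primary also at 1.10, primary fails and at least one secondary is falsely claimed: 0.975 − P(all three fail) = 4.3% at primary–MRSA correlation 0.5, and 3.7% at 0.8

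**What would a gate on the primary buy?** With all three outcomes at the margin, the chance of a false secondary claim drops to 0.6% to 1.2%. If the primary is truly non-inferior and passes, it stays at up to 4.9%. Only splitting alpha as well brings the ceiling to about 2.5%.

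**What would it cost?** Power for secondary non-inferiority at a true secondary HR of 0.95. Gated figures come from a bivariate normal with correlation 0.7 (MRSA) or 0.2 (bloodstream infection).

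| Outcome, SE | Primary's true HR | As planned | Gate | Gate and split |
|---|---|---|---|---|
| Bloodstream infection, 0.051 | 0.95 | 82% | 69% | 62% |
| Bloodstream infection, 0.051 | 1.0 | 82% | 40% | – |
| Bloodstream infection, 0.0765 | 0.95 | 48% | 42% | 32.5% |
| Bloodstream infection, 0.0765 | 1.0 | 48% | 26% | – |
| MRSA, 0.0765 | 0.95 | 48% | 47% | 37% |

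MRSA is shown only at the larger SE. The primary outcome is *S. aureus* "clinical cultures (MRSA + MSSA) where ICU-attributable is defined as" the cultures taken in the ICU window, so MRSA events are a subset of it. If precision follows event counts, a correlation of 0.7 means about 0.7² = 0.49 of the events and an SE about 1/0.7 = 1.4 times the primary's.

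**The case for a change.** The strongest case for a change is that the exemption from adjustment rests on a reason that does not apply to the test being exempted. The plan adjusts superiority for conservatism and leaves its main kind of claim unadjusted. A failed primary is not remote: on the figures above it happens 18% of the time at a true HR of 0.95 and 54% at 1.0. Bloodstream infection stands beside *S. aureus* cultures in the protocol's opening statement of aim, so a claim on it would be noticed. A gate takes no alpha from the primary, and keeping 95% intervals would preserve the view of possible harm.

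Part of this stands. The sentence does merge a non-inferiority test with a search for harm, and neither document says how a secondary non-inferiority result should be read after a failed primary. The rest is weaker. The two-sided test of a difference is in the plan: section 1.2.13 says superiority is already assessed within the primary analysis, and that same test can reject in the harmful direction. A reader who knows that the secondaries are unadjusted will treat them as supportive if the primary fails, which is ordinary practice.

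The gate also has a difficulty of its own. All-cause bloodstream infection covers all pathogens and asks a different question from *S. aureus* cultures, so missing a 10% margin on the primary does not make it uninformative. If secondary superiority were left outside the gate to protect it, the plan could claim superiority on an outcome while barring non-inferiority on it, although the first implies the second.

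**Conclusion.** No change to the plan follows. The observation about wording is correct, but it is a drafting slip: the reason belongs to the two-sided test for a difference, and the 10% margin rule is stated separately and clearly. Leaving the secondary non-inferiority tests unadjusted is a deliberate choice, disclosed in both documents. The SAP records that it was updated before the trial dataset was accessed.

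The exposure is limited. The primary conclusion is unaffected, each secondary test has a one-sided error of 2.5%, and the pair together stays at or below 5%. Gating or splitting alpha would trade part of that for a real loss of power, and the gate alone does not lower the ceiling when the primary passes. Rewriting the sentence or spelling out an inferiority rule would change no estimate, interval or test.

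The 5% bound needs no correlation assumption, but it does rest on reading two-sided 0.05 as an upper 95% limit against 1.10. Read as one-sided 0.05 per test, the bound for the pair would be 10%. The power figures depend on the inferred SE of 0.051, the assumed correlations and the 1.5-fold range; the documents give no power for either secondary outcome.

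### The two secondary superiority tests are validly fixed at 0.025 each; Holm's step-down would keep the same 0.05 family-wise bound and is never less powerful, for a small gain

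*Protocol*

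**What the plan says.** Protocol section 1.2.13 defines the family: "Secondary non-inferiority outcomes include 1) ICU-attributable MRSA clinical cultures and 2) ICU-attributable all-cause bloodstream infection". Non-inferiority on each is tested without multiplicity adjustment: "We will use two-sided significance tests set at alpha = 0.05 for each outcome to determine possible inferiority with greatest possible sensitivity". The margin is 10%, a hazard ratio of 1.10.

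Superiority comes second: "if non-inferiority is met for these secondary outcomes, we will perform a pre-specified assessment of superiority". The level is then given as an "assessment of superiority at a two-tailed significance set at alpha = 0.025, which accounts for the multiple comparisons of two outcomes". The section closes the topic by saying that "the superiority tests, if they are performed, will be adjusted for multiple testing, for conservatism".

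The Analysis part of the SAP gives the same rule with the same explanation, "which accounts for the multiple comparisons of two outcomes". Neither document mentions a step-down procedure or passing the level of a rejected test to the other test.

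**The concern.** Under the fixed rule each outcome is judged at 0.025 whatever the other shows. Suppose one outcome gives p = 0.01 and the other p = 0.03, both in favour of iodophor. The second must be reported as not superior, although a procedure with the same 0.05 guarantee would allow the claim. The sponsor included these tests because mupirocin resistance makes superiority plausible, so a rule that can only add rejections within the same guarantee deserves a look.

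Only the second rejection on secondary outcomes is at stake. The primary outcome is untouched, and the chance of at least one secondary superiority finding is the same under both rules.

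**Working it through.** **1. The plan's level.** 0.05 / 2 = 0.025, so this is Bonferroni for two tests. The bound is 0.025 + 0.025 = 0.05. If the tests were independent and both nulls true, the error would be 1 − 0.975² = 0.0494. The stated level is reproduced.

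**2. Holm's bound.**
- Both nulls true: any error needs the smaller p-value ≤ 0.025, which has probability at most 0.025 + 0.025 = 0.05.
- One null true: an error needs that test's own p ≤ 0.05, which has probability at most 0.05.

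Neither step uses the correlation. Any p ≤ 0.025 is rejected by Holm as well, so no Bonferroni rejection is lost.

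**3. Actual error.** Simulation with 1,000,000 draws per scenario, two-sided, before the non-inferiority condition is applied:

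| Situation | Bonferroni | Holm |
|---|---|---|
| Both nulls true, correlation 0 | 0.0496 | 0.0496 |
| Both nulls true, correlation 0.6 | 0.0453 | 0.0453 |
| One null true, other effect large | 0.025 | 0.050 |

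With the non-inferiority condition imposed (assumed SE of the log hazard ratio 0.05 or 0.10), the last row becomes about 0.0125 and 0.025, because only errors in favour of iodophor remain.

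**4. The non-inferiority condition.** A two-sided 0.05 superiority result for iodophor has a 95% upper limit below 1, hence below 1.10. That outcome's non-inferiority is then already met at the same level.

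**5. Standard errors.** The documents give no event counts or power for the secondary outcomes. The only anchor is the primary outcome: "With 120 hospitals, we will have 82% power to detect non-inferiority within a hazard ratio of 1.1", with a 5% advantage for iodophor, read here as a hazard ratio of 0.95. Inverting this:

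SE = (ln 1.10 − ln 0.95) / (1.960 + 0.915) = (0.0953 + 0.0513) / 2.875 = 0.051.

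The assumed event share relative to *S. aureus* is 40–60% for MRSA and 50–100% for bloodstream infection. With SE = 0.051 / √share, this gives 0.066–0.081 and 0.051–0.072.

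**6. Power.** Bonferroni power is Φ(|ln HR| / SE − 2.241). For MRSA at HR 0.85, |ln HR| = 0.1625. With SE 0.0806 this is Φ(2.016 − 2.241) = 41%; with SE 0.0658 it is Φ(2.469 − 2.241) = 59%. Holm adds, for one outcome, the probability that its statistic lies between 1.960 and 2.241 while the other exceeds 2.241, under a bivariate normal distribution.

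| True HR (MRSA / bloodstream) | Correlation | Quantity | Bonferroni | Holm |
|---|---|---|---|---|
| 0.95 / 0.95 | 0.2–0.6 | each outcome | – | +0.4 to +1.4 points |
| 0.90 / 0.90 | 0.2 | both shown | 5–14% | 9–21% |
| 0.85 / 0.85 | 0.2 | MRSA | 41–59% | 47–68% |
| 0.85 / 0.85 | 0.2 | both shown | 24–51% | 34–63% |
| 0.85 / 0.95 | 0.2 | MRSA | 41–59% | about +1 point |
| 0.85 / 0.95 | 0.2 | bloodstream infection | 6–11% | about 8.5–15% |

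**The case against.** The strongest reply is that nothing is wrong. The rule is valid, identical in both documents and described as conservative, so preferring Holm is a matter of efficiency. That stands, and it sets the weight of the point. It does not remove it: the remark about conservatism contrasts the adjusted superiority tests with the unadjusted non-inferiority tests, and Holm is still a full adjustment at 0.05. Neither document asks for a tighter bound.

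A reader might infer that Bonferroni gives up power for nothing. That is not so. When one effect is real and large and the other null is true, Bonferroni's error is half of Holm's. Only the guaranteed bound is the same.

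A reader might also infer a substantial loss of power. The plan's own assumption does not support that. The larger gains need a benefit on both outcomes of two or three times the planned 5%. The resistance rationale concerns *S. aureus*, whereas all-cause bloodstream infection covers all pathogens, and nothing in the documents supports an equal effect there. With a hazard ratio of 0.85 for MRSA and 0.95 for bloodstream infection, MRSA power barely moves.

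Finally, fixed 0.025 tests pair directly with 97.5% intervals. Holm has no equally simple counterpart, and the documents specify no interval level for these outcomes that would settle the matter. This cost is real.

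**Conclusion.** The plan's rule is correct and controls what it claims to control. Holm would be a modest improvement: the same family-wise bound of 0.05 under any correlation, every Bonferroni rejection retained, and some chance of a second rejection that the fixed rule forbids. These properties need no assumption.

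The size of the gain does rest on assumptions: the event shares, the correlations, and a standard error inverted from the primary outcome's stated power. On that footing it is about 0.4–1.4 points per outcome at the planned effect, and becomes material only if iodophor is clearly better on both outcomes. The documents do not support calling the present rule an error, a source of inflated error, or a serious loss of power.

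**What to change.** Replace the level in both protocol section 1.2.13 and the Analysis part of the SAP; changing only one would make them contradict each other. Suggested text:

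*Superiority on the two secondary outcomes will be tested by Holm's procedure at two-sided family-wise 0.05 (smaller p-value at 0.025; if significant, the other at 0.05). The family stays at two even if one outcome does not meet non-inferiority, and superiority is claimed for an outcome only if its own non-inferiority is met.*

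The second sentence matters. The present wording speaks of non-inferiority for the secondary outcomes in the plural and does not say what happens if only one meets it. With the family held at two, an outcome that fails non-inferiority counts as not rejected, so the other stays at 0.025.

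The cost is one sentence in each document, a short justification, and less simple simultaneous intervals. Because the new rule is more permissive, it is legitimate only before outcome data are accessed. The SAP's closing note places its own update after trial completion but before access to the dataset, so that revision was the natural point for the change. If outcome data have since been seen, the fixed 0.025 rule should stand.
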